1. INTRODUCTION

INCB 39110-206 is an open-label, single-group, Phase 1/2 study of INCB039110 in combination with ibrutinib in subjects with relapsed or refractory DLBCL. Phase 1 will evaluate the safety and tolerability of INCB039110 when combined with ibrutinib in subjects with DLBCL (ABC, GCB, or unclassifiable); Phase 2 will evaluate the efficacy of the combination in subjects with ABC or unclassifiable DLBCL at the dose determined in Phase 1. INCB039110 is a small molecule inhibitor of the JAK family of protein tyrosine kinases, with selectivity for JAK1. Members of the JAK family play an important role in signal transduction after cytokine and growth factor binding to their receptors; aberrant production of cytokines and growth factors has been associated with a number of cancers. Ibrutinib (IMBRUVICA[®]) is a first-in-class, potent, orally administered, covalently binding inhibitor of Bruton's tyrosine kinase. Ibrutinib has been approved in many regions, including the United States and Europe, for the treatment of patients with mantle cell lymphoma and CLL who have received at least 1 prior therapy, first-line treatment of patients with CLL with a deletion of the short arm of chromosome 17 (del17p) or a TP53 mutation, and patients with Waldenström's macroglobulinemia. Ibrutinib is currently under investigation in various indications as a single agent and in combinations.

A detailed description of the investigational product, target patient population, rationale for doses to be examined, and potential risks and benefits of treatment with INCB039110 and ibrutinib is provided in the Protocol, Section 1. The purpose of this SAP is to define the methodology for analyzing and summarizing the data collected during the conduct of Study INCB 39110-206.

2. STUDY INFORMATION, OBJECTIVES, AND ENDPOINTS

2.1. Protocol and Case Report Form Version

This SAP is based on INCB 39110-206 Protocol Amendment 5 dated 18 JUN 2020 and CRFs approved on 02 NOV 2016. Unless superseded by an amendment, this SAP will be effective for all subsequent Protocol Amendments and eCRF versions.

2.2. Study Objectives

2.2.1. Phase 1

2.2.1.1. Primary Objective

The primary objective of Phase 1 is to evaluate the safety and tolerability of INCB039110 in combination with ibrutinib in subjects with relapsed or refractory DLBCL.

2.2.1.2. Secondary Objective

The secondary objective of Phase 1 is to evaluate the efficacy of INCB039110 in combination with ibrutinib in terms of ORR.

[REDACTED]

- [REDACTED]
- [REDACTED]
- [REDACTED]

2.2.2. Phase 2

2.2.2.1. Primary Objective

The primary objective of Phase 2 is to evaluate the efficacy of INCB039110 in combination with ibrutinib in subjects with relapsed or refractory non-GCB DLBCL as demonstrated by ORR.

2.2.2.2. Secondary Objectives

The secondary objectives of Phase 2 are as follows:

- To evaluate efficacy in terms of DOR, durable response rate, PFS, and OS.
- To evaluate the safety and tolerability of the treatment combination.

[REDACTED]

- [REDACTED]
- [REDACTED]
- [REDACTED]

2.3. Study Endpoints

2.3.1. Phase 1

2.3.1.1. Primary Endpoint

Safety and tolerability will be assessed by evaluating the frequency, duration, and severity of AEs (including SAEs and DLTs), and changes in clinical and laboratory assessments.

2.3.1.2. Secondary Endpoints

Efficacy will be assessed by ORR, defined as the percentage of subjects achieving either a CR or PR.

[REDACTED]

- [REDACTED]
- [REDACTED]
- [REDACTED]

2.3.2. Phase 2

2.3.2.1. Primary Endpoint

Efficacy will be assessed by ORR, defined as the percentage of subjects achieving either a CR or PR.

2.3.2.2. Secondary Endpoints

- DOR, defined as the time from earliest date of disease response until earliest date of disease progression.
- Durable response rate, defined as the percentage of subjects achieving a CR or PR for > 16 weeks.
- PFS, defined as the time from enrollment until the earliest date of disease progression determined by objective radiographic disease assessments, or death due to any cause.
- OS, defined as the date of enrollment until death due to any cause.
- Safety and tolerability via assessment of the frequency, duration, and severity of AEs and SAEs, and changes in clinical and laboratory assessments.

[REDACTED]

- [REDACTED]
- [REDACTED]

3. STUDY DESIGN

3.1. Overall Study Design

This is an open-label, single-group, Phase 1/2 study of INCB039110 in combination with ibrutinib in subjects with relapsed or refractory DLBCL. Phase 1 will evaluate the safety and tolerability of INCB039110 when combined with ibrutinib in subjects with DLBCL (ABC, GCB, or unclassifiable) using a 6 + 3 design; Phase 2 will evaluate the efficacy of the combination in subjects with ABC or unclassifiable DLBCL at the dose determined in Phase 1 using a Simon 2-stage expansion design. Subjects may continue to receive study treatment until evidence of disease progression, unacceptable toxicity, or consent withdrawal.

[figure not shown]
3.1.1. Phase 1

The starting dose of INCB039110 will be 300 mg QD. Depending on tolerability, the dose of INCB039110 in combination with ibrutinib (560 mg QD) could be increased to 400 mg QD (Cohort 2) or decreased to 200 mg QD (Cohort -1). The dose selected for study in Phase 2 will be the dose tolerated by at least two-thirds of subjects who did not require a dose reduction within the first 28 days of treatment. In order to be included in the tolerability review, a subject must have received the cohort-specific dose of INCB039110 and ibrutinib for at least 75% of the days during the 28-day DLT surveillance period or have experienced a DLT. Additional subjects may be enrolled to achieve a minimum cohort size of 6 should withdrawal or dose interruptions/reductions result in a subject being nonevaluable. Dose cohorts are outlined in [Table 1](#), and the design is depicted in [Figure 1](#).

Table 1: Phase 1 Dose Cohorts

Cohort	Number	Regimen	Subjects With DLT	Action
-1	6	INCB039110 200 mg QD + ibrutinib 560 mg QD	≤ 1	Begin expansion portion of the study
			2	Enroll 3 additional subjects (9 subjects total)
			≥ 3	Terminate study
1 (Starting dose)	6	INCB039110 300 mg QD + ibrutinib 560 mg QD	≤ 1	Escalate to Cohort 2
			2	Enroll 3 additional subjects (9 subjects total); if no new DLTs, escalate to Cohort 2
			≥ 3	Reduce to Cohort -1
2	6	INCB039110 400 mg QD + ibrutinib 560 mg QD	≤ 1	Begin Phase 2 study
			2	Enroll 3 additional subjects (9 subjects total); if no new DLTs, begin Phase 2 study
			≥ 3	Begin Phase 2 study using Cohort 1 dose

[figure not shown]
Figure 1: Phase 1 Design Schema

3.1.2. Phase 2

Subjects with ABC or unclassifiable DLBCL will receive the recommended Phase 2 dose of INCB039110 in combination with ibrutinib as determined in Phase 1. Phase 2 will use a Simon 2-stage design with a stopping rule to allow early termination of the study at the end of Stage 1 if there is lack of sufficient efficacy. During Stage 1, if 9 or fewer of the first 22 evaluable subjects achieve an objective response (defined as a CR or PR), then the study may be terminated. If 10 or more subjects achieve an objective response, then the study will continue and accrue 38 additional subjects to Stage 2. Subjects who were enrolled but did not receive treatment will be excluded from the efficacy analysis and replaced. A timely assessment of response will be made to avoid risk of overenrollment before accrual to Stage 2. At the end of Stage 2, ORR will be assessed for sufficient efficacy to warrant further study. The study will be considered successful if the total number of objective responders is 29 or more. The design is depicted in Figure 2.

Figure 2: Phase 2 Design Schema

3.1.3. Definition of Dose-Limiting Toxicities

A DLT will be defined as the occurrence of any toxicities in Table 2 occurring up to and including Study Day 28, except those with a clear alternative explanation (eg, disease progression) or transient (≤ 72 hours) abnormal laboratory values without associated clinically significant signs or symptoms based on investigator determination. All DLTs will be assessed by the investigator using CTCAE v4.03 criteria (NCI 2010). In order to be included in the tolerability review, subjects must have received the cohort-specific dose of INCB039110 and ibrutinib for at least 75% of the days during the 28-day surveillance period or have experienced a DLT. Additional subjects may be enrolled to achieve a minimum cohort size should withdrawal or dose interruptions/reductions result in subjects being nonevaluable.

Table 2: Criteria for Defining Dose-Limiting Toxicity

Toxicity
Nonhematologic

 • Any \geq Grade 3 nonhematologic toxicity, EXCEPT the following: 
 – Transient (\leq 72 hours) abnormal laboratory values without associated clinically significant signs or symptoms. – Nausea, vomiting, and diarrhea adequately controlled with medical therapy within 48 hours. – Singular or nonfasting elevations in blood glucose (ie, blood glucose excursions will be considered toxicities if fasting blood glucose is elevated on 2 separate sequential occasions).
Hematologic

 • Grade 3 thrombocytopenia with bleeding. • Grade 4 thrombocytopenia. • Febrile neutropenia ($ANC < 1.0 \times 10^9/L$ and fever $> 101^\circ F/38.5^\circ C$). • Grade 4 neutropenia that does not recover to \leq Grade 2 in \leq 3 days after interrupting study drug. • Grade 4 anemia unresponsive to treatment. 
Note: "INCB039110 is suspected to cause transient decreases in ANC as a result of margination; therefore, DLT rules require neutropenia to persist after holding INCB039110 for 2 to 3 days. If the clinical status of the subject allows, investigators are encouraged to wait 24 hours before starting growth factors, to determine if white blood cell margination is contributing to the degree of neutropenia."

3.2. Level of Significance

The level of significance for the primary endpoint in Phase 2 is 1-sided 10%, which is deemed acceptable for a proof-of-concept study.

3.3. Sample Size Considerations

3.3.1. Sample Size for Phase 1

For Phase 1, the decision to de-escalate the dose will be driven by the number of observed toxicities and can be calculated based on the binomial distribution. A 6 + 3 dose escalation design will be used in this study.

3.3.2. Sample Size for Phase 2

The study will lead to a decision between 2 prespecified hypotheses about the probability of an ORR, p . The null hypothesis $H_0: p = 40\%$ reflects a response rate that would be of no clinical benefit, and the alternative hypothesis $H_A: p = 55\%$ is a response rate that might lead to larger, confirmatory studies. Using a Simon 2-stage optimal design, a total of 60 subjects will be needed for 80% power at 1-sided $\alpha = 0.1$ level. If there are ≤ 9 objective responders from the first 22 evaluable subjects, then this will support the null hypothesis, and the study will be terminated. Otherwise, 38 additional subjects will be enrolled (Stage 2).

3.4. Schedule of Assessments

All study assessments will be performed as indicated in the schedule of assessments in Table 8 of Protocol Amendment 5 (dated 18 JUN 2020); the order of assessments is suggested by the order of mention within the schedule. Laboratory assessments are shown in Table 9 of Protocol Amendment 5 (dated 18 JUN 2020).

4. DATA HANDLING DEFINITIONS AND CONVENTIONS

4.1. Scheduled Study Evaluations and Study Periods

4.1.1. Day 1

Day 1 is the date of first dose of INCB039110 or ibrutinib.

4.1.2. Study Day

The study day at a visit or reporting date will be calculated by the visit or reporting date minus the Day 1 date plus 1 (visit date – Day 1 date + 1). This study day will be subtracted by 1 if it is ≤ 0 , so that a study day of 0 will never occur. A study day of -1 indicates 1 day before Day 1.

4.1.3. Scheduled Visits

Study evaluations in weeks or days from Day 1 are presented in the Schedule of Assessments.

4.1.4. Baseline Assessments

Baseline is defined as the last nonmissing measurement obtained before the first dose of INCB039110 or ibrutinib is administered.

4.1.5. Last Available Value

The last available value is the last nonmissing measurement obtained after starting INCB039110 or ibrutinib and within 90 days after the last dose of INCB039110 or ibrutinib.

4.2. Variable Definitions

4.2.1. Prior and Concomitant Medication

Prior medication is defined as any nonstudy drug started before the first dose of INCB039110 or ibrutinib.

Concomitant medication is defined as any nonstudy drug that is started accordingly:

- Before the date of first administration of INCB039110 or ibrutinib and is ongoing throughout the study or ends on/after the date of first study drug administration.
- On/after the date of first administration of INCB039110 or ibrutinib and is ongoing or ends during the course of study drug administration.

Note: A prior medication could also be classified as "both prior and concomitant medication" if the end date is on or after first dose of INCB039110 or ibrutinib. In the listing, it will be indicated whether a medication is prior-only, concomitant-only, or both prior and concomitant medication.

The start/stop dates recorded in the eCRF by the investigator and his or her research staff will be used to identify when a concomitant medication was taken during the study. Any missing start date must be queried for resolution. Unresolved missing start dates will be handled as follows:

- If the date is completely missing, then the medication will be considered both prior and concomitant.
- If only the day is missing, and the last day of the month is before the first dose date on Day 1, then the concomitant medication will be considered as starting before Day 1, and the incomplete date will be imputed as the last day of the month.
- If only the day is missing, and the first day of the month is after the first dose date on Day 1, then the concomitant medication will be considered as starting after Day 1, and the incomplete date will be imputed as the first day of the month.
- If only the day is missing, and the month is equal to the month of the first dose date on Day 1, then the incomplete date will be imputed as the first day of the month.
- If both the month and day are missing, and the last day of the year is before the first dose date on Day 1, then the concomitant medication will be considered as starting before Day 1, and the incomplete date will be imputed as if it is the last day of the year. Otherwise, the incomplete date will be imputed as if it is the first day of the year.

5. STATISTICAL METHODOLOGY

5.1. General Methodology

Unless otherwise noted, SAS[®] software (SAS Institute Inc, Cary, NC; version 9.1 or later) will be used for the generation of all tables, graphs, and statistical analyses. Descriptive summaries for continuous variables will include, but not be limited to, the number of observations, mean, standard deviation, median, minimum, and maximum. Descriptive summaries for categorical variables will include the number and percentage of subjects in each category.

For the Phase 1 portion of the study, the safety run-in population (defined in Section 5.3.3) will be used for all safety analyses. For the Phase 2 portion of the study, the safety evaluable population will be used for all safety analyses, and the ITT population will be used for all efficacy analyses. [REDACTED]

5.2. Treatment Groups

Subjects will be summarized overall and based on the dose regimen initially assigned:

- Ibrutinib 560 mg QD + INCB039110 200 mg QD
- Ibrutinib 560 mg QD + INCB039110 300 mg QD
- Ibrutinib 560 mg QD + INCB039110 400 mg QD

Table summaries, unless otherwise indicated, will be provided by treatment group. Note that 1 of the above 3 treatments will be recommended for Phase 2 of the study, and separate summaries will be provided for the Phase 1 and Phase 2 portions of the study.

5.3. Analysis Populations

5.3.1. Intent-to-Treat Population

The ITT population will include all subjects enrolled into the Phase 2 portion of the study. This population will be used for analyses of all efficacy data.

5.3.2. Per Protocol Population

The PP population for efficacy data will include subjects in the ITT population who are considered to be compliant with the Protocol and will be defined for supportive sensitivity analyses for the primary and secondary efficacy endpoints. This population will include subjects in the ITT population who received at least 80% of the assigned study drug regimen, met all inclusion/exclusion criteria, and had no significant Protocol violations as determined by sponsor. A subject who is discontinued because of disease progression is considered to be evaluable for the PP population.

5.3.3. Safety Population

The safety run-in population will include all subjects enrolled in the Phase 1 portion of the study who received at least 1 dose of study drug. The safety evaluable population will include all subjects enrolled in the Phase 2 portion who received at least 1 dose of study drug. Treatment

groups for this population will be determined according to the actual treatment that the subject receives on Day 1. All safety analyses in Phase 1 and 2 will be conducted using the safety run-in population and safety evaluable population, respectively.

[REDACTED]

6. BASELINE, EXPOSURE, AND DISPOSITION VARIABLES AND ANALYSES

A list of planned tables, figures, and listings is provided in [Appendix B](#).

6.1. Baseline and Demographics, Physical Characteristics, and Disease History

The following demographic and baseline characteristics will be summarized for the safety run-in/safety evaluable populations: age, sex, race, ethnicity, weight, height, ECOG performance status, prior radiation (yes/no), prior surgery (yes/no), prior treatment regimens, number of prior treatment regimens, subtype of DLBCL, B symptoms, and bulky disease (≥ 10 cm).

6.2. Disposition of Subjects

The number and percentage of subjects who were enrolled and who were withdrawn from the study (with a primary reason for withdrawal) will be summarized for the ITT and safety run-in/safety evaluable populations.

6.3. Protocol Deviations

Protocol deviations captured on the Protocol Deviation Log will be presented in the subject data listings.

6.4. Exposure

For subjects in the ITT and safety run-in/safety evaluable populations, exposure to INCB039110 and ibrutinib will be summarized descriptively as follows:

- **Duration of treatment (days):** The duration of treatment will be number of study days between Day 1 and the last nonzero dose administration record of INCB039110 or ibrutinib taken by the subject.
- **Average daily dose of INCB039110 or ibrutinib (mg/day):** Average daily dose of study drug (mg/day) = [total actual study drug taken (mg)] / [duration of treatment with study drug (days)].

6.5. Study Drug Compliance

For subjects in the ITT and safety run-in/safety evaluable populations, overall compliance (%) for INCB039110 or ibrutinib will be calculated for all subjects as follows:

$$\text{overall compliance (\%)} = 100 \times (\text{total dose taken}) / (\text{intended dose})$$

The intended dose will be determined up to the earliest study day of permanent discontinuation of INCB039110 or ibrutinib (ie, AE discontinuation is the first AE with action taken being "drug withdrawn"), last study drug record in the database, or subject death. Intended dose is defined as the sum of the doses prescribed by the investigator accounting both for planned dose reductions as well as those reductions or increases mandated by the investigator.

6.6. Medical History

For subjects in the ITT and safety run-in/safety evaluable populations, medical history will be summarized by assigned treatment group. This summation will include the number and percentage of subjects with significant medical history for each body system/organ class and documented on the Medical History eCRF.

6.7. Prior and Concomitant Medication

For subjects in the safety run-in/safety population, prior medications and concomitant medications will be coded using the WHO Drug Dictionary and summarized by WHO drug class and WHO drug term. In the data listing, each medication will be recorded as prior, concomitant, or both prior and concomitant. Results will be summarized as number and percentage of subjects with prior and concomitant medications by preferred term and WHO drug class.

Prior medication information will also be used to identify anticancer medication received by subjects before enrollment into the study. Prior anticancer medication data will be summarized and presented by treatment group as well as listed.

7. EFFICACY

A list of planned tables, figures, and listings is provided in [Appendix B](#).

7.1. General Considerations

Not applicable.

7.2. Efficacy Hypotheses

Objective response rate (primary endpoint): Administration of INCB039110 in combination with ibrutinib increases ORR in subjects with relapsed or refractory non-GCB DLBCL compared with historical rate.

7.3. Analysis of the Primary Efficacy Parameter

7.3.1. Primary Efficacy Analysis

The primary variable for the Phase 2 of the study is ORR, which is defined as the proportion of subjects with best response (CR or PR) by modified Lugano Classification ([Cheson et al 2014](#)) for DLBCL. The proportion of responders within each treatment group will be estimated with 90% CIs by treatment group. Confidence intervals will be calculated based on the method of Koyama and Chen ([2008](#)) that accounts for early termination rules of the Simon 2-stage design. Within each treatment group, 1- sample binomial test will be used to test the null hypothesis.

In general, best response is determined on the subject level using the highest overall response achieved postbaseline. In the case of SD, measurements must meet the SD criteria at least once after study entry at a minimum interval of 56 days. Subjects who fail to meet these criteria will have best response of PD if the next available Lugano Classification evaluation after the initial scan indicates PD or NE if no additional evaluations are available.

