Subjects with ABC or unclassifiable DLBCL will receive the recommended Phase 2 dose of INCB039110 combination with ibrutinib as determined in Phase 1. Phase 2 will use a Simon 2-stage design with a stopping rule to allow early termination of the study at the end of Stage 1 if there is lack of sufficient efficacy. During Stage 1, if 9 or fewer of the first 22 evaluable subjects achieve an objective response (defined as a CR or PR), then the study may be terminated. If 10 or more subjects achieve an objective response, then the study will continue and accrue 38 additional subjects to Stage 2. Subjects who were enrolled but did not receive treatment will be excluded from the efficacy analysis and replaced. A timely assessment of response will be made to avoid risk of overenrollment before accrual to Stage 2. At the end of Stage 2, ORR will be assessed for sufficient efficacy to warrant further study. The study will be considered successful if the total number of objective responders is 29 or more. The study will end once all subjects have discontinued study treatment.

Study Population:

Key Inclusion Criteria:

- Male or female, 18 years or older.
 - Histologically documented diagnosis of DLBCL.
 - For Phase 1, subjects may have any DLBCL subtype.
 - For Phase 2, subjects must have ABC or unclassifiable subtypes of DLBCL confirmed by immunohistochemistry using the Hans algorithm.
- Subjects having a computed tomography (CT) scan abnormality with uncertain interpretation following completion of the most recent treatment regimen must have biopsy confirmation of residual DLBCL before study entry.
- Relapsed or refractory DLBCL, defined as having received at least 1 but no more than 3 prior treatment regimens and ineligible for high-dose chemotherapy/autologous stem cell transplant.
 - Fluorodeoxyglucose-avid disease (based on local evaluation) per the Lugano Classification. Fluorodeoxyglucose-avid disease is defined as disease with a 5-point scale score of 4 or 5.
 - Subjects must have archived tumor tissue (block or 15-20 unstained slides) available, or be willing to undergo an incisional or excisional lymph node biopsy of accessible adenopathy (or, in less accessible lymph nodes, 4 to 8 core biopsies).

- At least 1 measurable (≥ 2 cm in longest dimension) lesion on CT scan or magnetic resonance imaging (MRI).
- Eastern Cooperative Oncology Group (ECOG) performance status 0 to 2.

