The study will lead to a decision between 2 prespecified hypotheses about the probability of an ORR, p . The null hypothesis H_0 : $p = 40\%$ reflects a response rate that would be of no clinical benefit, and the alternative hypothesis H_A : $p = 55\%$ is a response rate that might lead to larger, confirmatory studies. Using a Simon 2-stage optimal design, a total of 60 subjects will be needed for 80% power at 1-sided $\alpha = 0.1$ level. If there are 9 or fewer objective responders from the first 22 evaluable subjects, the null hypothesis will be considered as supported, and the study will be terminated. Otherwise, 38 additional subjects will be enrolled (Stage 2). Subjects who did not receive study treatment will be excluded from the analysis of Stage 1 and replaced.

Primary efficacy analysis: The study will be considered successful if the total number of objective responders is ≥ 29 in Phase 2. A 90% confidence interval will be calculated for the ORR.

Secondary efficacy [REDACTED] analysis: Median DOR and durable response rate (CR or PR ≥ 16 weeks) will be estimated with a 90% confidence interval. Median PFS will be estimated with 90% confidence intervals. [REDACTED]

Safety Analysis: Safety data will be tabulated with summary statistics.

TABLE OF CONTENTS

SYNOPSIS	3
LIST OF ABBREVIATIONS.....	16
1. INTRODUCTION	19
1.1. Overview of Diffuse Large B-Cell Lymphoma.....	19
1.1.1. Treatment for Advanced DLBCL	20
1.1.2. Treatment for Relapsed/Refractory DLBCL	21
1.2. Study Rationale.....	21
1.2.1. Inhibition of Janus Kinase as a Target for Cancer Therapy	21
1.2.2. Inhibition of JAK With INCB039110	23
1.2.3. Inhibition of Bruton's Tyrosine Kinase as a Target for Cancer Therapy.....	24
1.2.4. Combined Inhibition of JAK and BTK in DLBCL	25
1.3. Potential Risks and Benefits of the Treatment Regimen	26
1.3.1. INCB039110.....	26
1.3.2. Ibrutinib	27
1.3.2.1. Summary of Clinical Safety.....	27
1.3.2.2. Risks	28
1.3.2.3. Cytopenias	28
1.3.2.4. Atrial Fibrillation.....	28
1.3.2.5. Second Primary Malignancies	28
1.3.2.6. Tumor Lysis Syndrome	28
1.3.2.7. Diarrhea	29
1.3.2.8. Rash	29
1.3.2.9. Interstitial Lung Disease	29
1.3.3. Potential Risks and Benefits for the Combination of INCB039110 and Ibrutinib	29
2. STUDY OBJECTIVES AND ENDPOINTS.....	30
2.1. Study Objectives.....	30
2.1.1. Phase 1	30
2.1.1.1. Primary Objective.....	30
2.1.1.2. Secondary Objective.....	30
██████████	30
2.1.2. Phase 2.....	30

2.1.2.1.	Primary Objective.....	30

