4.3. Number of Subjects

4.3.1. Planned Number of Subjects

Up to 18 subjects will be enrolled in Phase 1, and approximately 60 subjects will be enrolled in Phase 2 (22 in Stage 1 and 38 in Stage 2).

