9.4. Statistical Analyses

9.4.1. Primary Analyses

The primary endpoint is ORR; a subject will be considered as a responder if his or her best overall response is PR or better based on the Lugano Classification (Cheson et al 2014). The rate of responders will be estimated using the observed rate, and its 90% CI will be calculated using the method of Koyama and Chen (2008) that accounts for the early termination rules of the Simon 2-stage design. The study will be considered successful if the total number of objective responders is ≥ 29 in Phase 2.

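### SAP 7.3.1 tests H0 with a binomial test of unstated version, unadjusted for the Stage 1 stop; at exactly 29/60, a declared success, its one-sided p-value can be 0.118 rather than the two-stage 0.095

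*SAP*

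**What the plan says.** The null and alternative response rates are 40% and 55% (Protocol 9.2.2, SAP 3.3.2). The level is one-sided 10% (Protocol 9.3, SAP 3.2). Stage 1 enrols 22 evaluable subjects, and the trial continues with 10 or more responders. Stage 2 adds 38 subjects.

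The success criterion is a count. SAP 3.1.2 states: "The study will be considered successful if the total number of objective responders is 29 or more". Protocol 9.4.1 states: "The study will be considered successful if the total number of objective responders is ≥ 29 in Phase 2".

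SAP 7.3.1 gives the 90% confidence interval by a method "that accounts for early termination rules of the Simon 2-stage design". The next sentence reads: "Within each treatment group, 1- sample binomial test will be used to test the null hypothesis". Nothing there or elsewhere in the SAP gives the version of this test, adjusts it for the Stage 1 stop, or relates it to the count of 29. Protocol 9.4.1 names no test beyond the count.

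The documents also differ on what happens with 9 or fewer responders in Stage 1. The Protocol synopsis (study design) and Protocol 4.1.2 say that if too few subjects "achieve an objective response (defined as a CR or PR), then the study may be terminated"; SAP 3.1.2 agrees. The synopsis section on sample size says "the null hypothesis will be considered as supported, and the study will be terminated", and Protocol 9.2.2 and SAP 3.3.2 likewise make the stop definite.

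**The concern.** A two-stage design controls its type I error partly through the Stage 1 stop. A trial with 9 or fewer responders among the first 22 cannot go on to reach 29. A one-sample binomial test on 60 subjects ignores this and counts those paths as if they could still end in rejection, so its p-value at a given total is larger than the design's own.

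A statistician could follow SAP 7.3.1 faithfully and obtain a primary-endpoint p-value above or below 0.10 at 29 responders, depending on a choice the plan leaves open. The report could then show a declared success beside a p-value that does not reject H0 at the plan's own level, exactly at the decision boundary.

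**Working it through.** **Inputs.** p0 = 0.40, p1 = 0.55, one-sided level 0.10, 22 + 38 = 60 subjects, continue if X1 ≥ 10, success if the total is ≥ 29 (SAP 3.1.2, 3.2 and 3.3.2; Protocol 9.2.2 and 9.4.1).

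**1. Reproduce the design.** With X1 ~ Bin(22, p) and X2 ~ Bin(38, p), the probability of success is P(X1 ≥ 10 and X1 + X2 ≥ 29).
- At p = 0.40 it is 0.0949 (type I error).
- At p = 0.55 it is 0.8004 (power).

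A search over two-stage designs up to N = 70 returns exactly this one as optimal: stop at ≤ 9/22, fail at ≤ 28/60. The plan's design and cut-off reproduce.

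**2. One-sided p-values against 40%, by version of the test.** The exact test uses P(Bin(60, 0.40) ≥ k). The uncorrected normal test uses z = (k/60 − 0.40)/√(0.24/60); the corrected version subtracts 0.5/60 from the numerator. At k = 29, z is 1.318 and 1.186.

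| Total k | Two-stage tail | Exact binomial | Normal, continuity-corrected | Normal, uncorrected |
|---|---|---|---|---|
| 28 | 0.1341 | 0.1779 | 0.1782 | 0.1459 |
| 29 | 0.0949 | 0.1184 | 0.1178 | 0.0938 |
| 30 | 0.0630 | 0.0746 | 0.0736 | 0.0569 |

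All four exceed 0.10 at 28 and all are below it at 30. They split only at 29. Two less usual versions at 29, mid-p (0.0965) and a Wald statistic (0.0982), also fall below 0.10.

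**3. Source of the gap.** 0.1184 − 0.0949 = 0.0235. This is the probability under H0 of reaching 29 or more of 60 with 9 or fewer responders in Stage 1, which the stop rules out.

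**4. If the exact test governed.** Rejection would need 30 responders. With the stop applied, type I error would be 0.0630 and power 0.757.

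**5. How often it matters.** P(X1 ≥ 10 and total = 29) is 0.0949 − 0.0630 = 0.0318 at p = 0.40 (unrounded difference) and 0.8004 − 0.7567 = 0.0437 at p = 0.55.

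**6. The confidence interval.** The SAP does not print the formula, so assume that the lower limit solves P(X1 ≥ 10 and total ≥ k | p) = 0.05. It is then 37.9% at 29, 39.3% at 30 and 40.7% at 31. The two-sided 90% interval therefore includes 40% at 29 and at 30.

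**7. Dependence on the stop.** If the stop is not applied, the type I error of 29 or more of 60 is the single-stage tail, 11.8%.

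**The case against.** The strongest answer is that no decision is affected. Success is a count of 29 or more, stated consistently in both documents, and no passage lets the binomial test decide. This stands. It is why the point is minor.

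It can also be said that the SAP sentence only names the test family, with the boundary set in SAP 3.1.2. That reading is possible, but no passage ties the test to that boundary, and the sentence sits in the primary analysis section as the test of H0.

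Nor is it certain that a p-value will be shown. For the primary endpoint, SAP Appendix B lists only summaries of best response, and the table shells were removed. That limits the claim to what the report could show.

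Finally, if the stop is not binding, the unadjusted exact p-value is the appropriate one. This is correct. The two-stage p-value is valid only once the conflict over the stop is resolved.

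Two stronger readings are tempting. One is that the unadjusted test inflates the false-positive rate. It does not: the exact test is conservative under either wording of the stop. The other is that the cut-off of 29 is wrong. It reproduces as the optimal design when the stop is applied.

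**Conclusion.** The concern holds as a minor defect in specification. H0, the level, the side and the test family are given; the version of the test and its adjustment for the Stage 1 stop are not. At 29 of 60 the resulting p-value is 0.118 or 0.094, against 0.095 for the design. The word normal alone does not settle it, because the two normal versions fall on opposite sides of 0.10.

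A reader might infer that the binomial test overrides the count, raising the bar to 30. The documents do not say so; the 75.7% power figure applies only if it did. A reader might also take the 90% interval as a second success criterion. No passage uses it that way.

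The figures assume 60 subjects analysed and, for the two-stage values, that the Stage 1 stop is applied. The interval limits also rest on the assumed tail inversion. What to do if the number analysed is not 60 is a separate matter. It first requires settling which number applies, since SAP 5.3.1 includes everyone enrolled in Phase 2 while SAP 3.1.2 excludes and replaces untreated subjects.

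**What to change.** 1. In SAP 7.3.1, replace the binomial-test sentence with: *H0 is rejected if Stage 1 is passed (≥ 10 of 22) and total responders are ≥ 29 of 60; the one-sided p-value reported is the two-stage tail probability P(X1 ≥ 10 and total ≥ observed | p = 0.40).* Writing out the formula matters, because both documents cite the named method for the interval only and neither says that it supplies a p-value.

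2. Add one sentence: the two-sided 90% confidence interval is for estimation and does not decide success.

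3. Reconcile the permissive and definite wording on the Stage 1 stop in the Protocol (synopsis, 4.1.2, 9.2.2) and the SAP (3.1.2, 3.3.2), since the p-value in item 1 assumes that the stop is applied.

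Items 1 and 2 cost two SAP sentences. Item 3 needs a Protocol clarification as well as a SAP edit. None of them changes the sample size, the cut-off, data collection or anything asked of patients.
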